7.5 Dose Modification for Hepatic Impaired Subjects

Subjects who develop acute hepatic toxicity with liver enzymes Grade 3 or higher while on study should be managed per standard dose modification guidelines in Section Error! Reference source not found. Ibrutinib is metabolized in the liver. In the population PK analysis (1,202 subjects), 179 subjects (14.9%) had mild hepatic impairment according to National Cancer Institute criteria and 12 subjects (1.0%) had moderate hepatic impairment. These subjects did not show a significantly higher ibrutinib exposure compared with subjects with normal hepatic function. In a hepatic impairment study, data showed an increase in ibrutinib exposure. For subjects with mild liver impairment (Child-Pugh class A), the recommended dose is 280mg daily. For subjects with moderate liver impairment (Child-Pugh class B), the recommended dose is 140mg daily. Monitor subjects for signs of ibrutinib toxicity and follow dose modification guidance as needed. It is not recommended to administer ibrutinib to subjects with severe hepatic impairment Subjects with clinically significant chronic hepatic impairment at the time of Screening (Child- Pugh class C) are excluded from study participation. Concomitant use of strong CYP inhibitors is not permitted in subjects with chronic hepatic impairment. Refer to Appendix D for Child-Pugh classification. Please refer to Table 3 for dose modifications due to hepatic impairment.

Table 1. Dose Modification Guidance for Hepatic Impaired Subjects

Child Pugh	class A	Child Pugh Cla	Child Pugh			
(Mild hepat	ic	(Moderate hepa	class C			
impairment)*	impairment)**	(Severe hepatic			
			impairment)			
Ongoing at	Develops	Ongoing at	Develops	Develops during		
time of	during	time of	during study	study		
enrollment	study	enrollment				

Ibrutinib	280 mg	280mg	140 mg	140 mg	Hold until
Dose					improves to
(daily)					moderate [Class
					B] or better)

^{*} If further reduction is needed due to non-hepatic toxicity, dose may be reduced to 140 mg. In the event that additional reduction is needed, ibrutinib should be held for non-hepatic toxicity until resolution.

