4.0 STUDY POPULATION

4.1 Inclusion criteria.

- 1. Diagnosis of CLL/SLL that meets IWCLL diagnostic criteria.(7)
- Patients must be aged over 18 years at the time of informed consent, understand and voluntarily sign an informed consent, and be able to comply with study procedures and follow-up examinations.
- 3. No treatment indication according to IWCLL criteria.(7)
- 4. Estimated time to first treatment of 3 years or less according to MDACC nomogram.(3)
- 5. ECOG performance status of 0-2.(27)
- 6. Male and female subjects who agree to use both a highly effective method of birth control (e.g., implants, injectables, combined oral contraceptives, some intrauterine devices [IUDs], complete abstinence¹, or sterilized partner) and a barrier method (e.g., condoms, vaginal ring, sponge, etc.) during the period of therapy and for 30 days after the last dose of study drug for females and 90 days for males. OR Female subjects who are of non-reproductive potential (i.e., postmenopausal by history no menses for ≥1 year; OR history of hysterectomy; OR history of bilateral tubal ligation; OR history of bilateral oophorectomy).
- 7. Adequate hepatic and renal function as indicated by all of the following: Total bilirubin </=1.5 x institutional Upper Limit of Normal (ULN) except for patients with bilirubin elevation due to Gilbert's disease or of non-hepatic origin who will be allowed to participate; an ALT </=2.5 x ULN; and estimated creatinine clearance

About HMA/Working Groups/CTFG/2014 09 HMA CTFG Contraception.pdf

Protocol 2017-0039. Ibrutinib early treatment for high-risk CLL. Version 11, 19Dec2022

Page 8 of 43

¹ Complete abstinence is a highly effective method only if defined as refraining from heterosexual intercourse during the entire period of risk associated with the study treatments. The reliability of sexual abstinence needs to be evaluated in relation to the duration of the clinical trial and the preferred and usual lifestyle of the subject. http://www.hma.eu/fileadmin/dateien/Human_Medicines/01

- (CrCl) of > 30 mL/min, as calculated by the Cockroft- Gault equation unless disease related.
- 8. PT/INR <1.5 x ULN and PTT (aPTT) <1.5 x ULN (unless abnormalities are unrelated to coagulopathy or bleeding disorder).

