- 9. Free of prior malignancies for 3 years with exception of patients diagnosed with basal cell or non-metastatic squamous cell carcinoma of the skin, or carcinoma "in situ" of the cervix or breast, who are eligible even if they are currently treated or were treated and/or diagnosed in the past 3 years prior to study enrolment.
- 10. A negative urine pregnancy test (within 7 days of enrollment date) is required for women with childbearing potential. Women of childbearing potential include any female who has experienced menarche and who has not undergone successful surgical sterilization (hysterectomy, bilateral tubal ligation, or bilateral oophorectomy) or is not postmenopausal (≥1 year of no menses, by history).

4.2 Exclusion criteria.

- Receipt of any prior therapy for CLL. Patients who have received "early intervention" with INVAC-1 vaccine against hTERT will be eligible provided all the following exist:
 - i) They had no response to the vaccine treatment (persistent CLL >1% in bone marrow).
 - ii) ≥3 months have elapsed since the last dose of vaccine.
 - iii) No residual toxicities attributable to the vaccine exist at the time of study enrollment.
 - iv) The patient does not meet IWCLL criteria for requiring treatment.
- 2. Richter transformation.
- 3. Active malignancy requiring systemic therapy, other than CLL, with the exception of: adequately treated in situ carcinoma of the cervix uteri; adequately treated basal cell carcinoma or localized squamous cell carcinoma of the skin; previous malignancy confined and surgically resected (or treated with other modalities) with curative intent.
- 4. Systemic anticoagulation with warfarin or other Vitamin K antagonists.
- 5. Active and uncontrolled autoimmune hemolytic anemia (AIHA) or autoimmune thrombocytopenia (ITP) requiring daily prednisone dose of >20 mg.
- 6. Current and concurrent use of strong CYP3A4 inhibitors or activators.
- 7. Pregnant or breast-feeding females.

- 8. Uncontrolled and active systemic fungal, bacterial, viral, or other infection (defined as exhibiting ongoing signs/symptoms related to the infection and without improvement, despite appropriate antibiotics or other treatment).
- Any other severe concurrent disease, or history of serious organ dysfunction or disease involving the heart, kidney, liver or other organ system that, in the investigator's opinion, may place the patient at undue risk to undergo therapy with ibrutinib.

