- 10. Currently active, clinically significant cardiovascular disease, such as uncontrolled arrhythmia or Class 3 or 4 congestive heart failure as defined by the New York Heart Association Functional Classification; or a history of myocardial infarction, unstable angina, or acute coronary syndrome within 6 months prior to randomization.
- 11. History of ischemic stroke within 6 months prior to enrollment.
- 12. Evidence of bleeding diathesis or coagulopathy within 3 months (e.g., von Willebrand's disease or hemophilia).
- 13. Any history of symptomatic intracranial hemorrhage.
- 14. Major surgical procedure with 4 weeks of first dose of study drug; open biopsy, or significant traumatic injury within 7 days prior to enrollment date; anticipation of need for major surgical procedure during the course of the study.
- 15. Minor surgical procedures, fine needle aspirations or core biopsies within 3 days prior to enrollment date. Bone marrow aspiration and/or biopsy are allowed.
- 16. Serious, non-healing wound, ulcer, or bone fracture.
- 17. Vaccinated with live, attenuated vaccines within 4 weeks of first dose of study drug.
- 18. Active, uncontrolled infection.
- 19. Known history of human immunodeficiency virus (HIV) or active with hepatitis C virus (HCV) or hepatitis B virus (HBV). Subjects who are positive for hepatitis B core antibody, hepatitis B surface antigen, or hepatitis C antibody must have a negative polymerase chain reaction (PCR) result before enrollment. Those who are PCR positive will be excluded.
- 20. Currently active, clinically significant hepatic impairment Child-Pugh class B or C according to the Child Pugh classification (see Appendix L)

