6.4 Pharmacokinetics and Product Metabolism

Following oral administration of ibrutinib at doses ranging of 420, 560, and 840 mg/day, exposure to ibrutinib increased as doses increased with substantial intersubject variability. The mean half life $(t_{1/2})$ of ibrutinib across 3 clinical studies ranged from 4 to 6 hours, with a median time to maximum plasma concentration (T_{max}) of 1 to 2 hours. Taking into account the approximate doubling in mean systemic exposure when dosed with food and the favorable safety profile, ibrutinib can be dosed with or without food. Ibrutinib is extensively metabolized primarily by CYP 3A4-mediated metabolic pathways. The on-target effects of metabolite PCI-45227 are not considered clinically relevant. Steady-state exposure of ibrutinib and PCI-45227 was less than 2-fold of first dose exposure. About 8% of ibrutinib is excreted renally. Ibrutinib exposure is not altered in patients with creatinine clearance (CrCl) >30 mL/min. Patients with severe renal impairment or patients on dialysis have not been studied. Following single dose administration, the AUC of ibrutinib increased 2.7-, 8.2and 9.8-fold in subjects with mild (Child-Pugh class A), moderate (Child-Pugh class B), and severe (Child-Pugh class C) hepatic impairment compared to subjects with normal liver function. A higher proportion of Grade 3 or higher adverse reactions were reported in patients with B-cell malignancies (CLL, MCL and WM) with mild hepatic impairment based on NCI organ dysfunction working group (NCI-ODWG) criteria for hepatic dysfunction compared to patients with normal hepatic function.

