15.0 STATISTICAL CONSIDERATIONS

- **15.1** This is a phase II single arm study of ibrutinib monotherapy in early stage CLL with a predicted time-to-treatment interval of less than 3 years, according to the MDACC nomogram developed by Wierda et al.(4) The primary objective is to evaluate the CR/CRi rate at two years. A maximum of 50 patients will be enrolled in the study with an estimated accrual rate of 4 patients per month; the accrual duration will be approximately 1 year.
- **15.2** The historical CR/CRi rate for patients who are treated when they have symptomatic disease requiring therapy, in the first line setting is 16% at 2 years (Pharmacyclics, internal data). We expect that early therapy with ibrutinib may increase this CR/CRi rate at two years from 16% to 30%. A sample size of 50 patients achieves 78% power to detect a difference of 14% in the 2-yr complete remission rate (i.e. to double the remission rate) using a one-sided binomial test. The target significance level is 0.05. These results assume that the population proportion under the null hypothesis is 16%.
- **15.3** For the primary analysis, we will calculate the proportion of patients with CR/CRi at 24 months, along with 95% confidence intervals. We will test the observed 2-year rate versus the null hypothesis of a 16% rate using a one-sided exact binomial test.
- 15.4 For secondary analyses, proportions of patients with objective response at 6, 12 and 24 months and CR/CRi at 6 and 12 months will be estimated along with 95% confidence intervals. The Kaplan-Meier method will be applied to estimate the progression free survival (PFS), the time to best response, the time to CR/CRi and time-to-alternative treatment survival curves. We will calculate the median time as well as the 2-year and 5-year survival rate and the corresponding 95% confidence intervals. In addition, we will directly compare the observed PFS time to each patient's individual predicted PFS time.

Protocol Amendments

Any amendments to the Protocol or Informed Consent Form must be sent to Pharmacyclics for review and approval prior to submission to the IRB. Written verification of IRB approval will be obtained before any amendment is implemented.

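### Section 7.5 names only Child-Pugh class C as excluded at screening and tabulates a starting dose for class B, although exclusion 20 bars class B and class C

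*Combined protocol and SAP*

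**What the plan says.** Section 4.2, exclusion 20, bars patients with "Currently active, clinically significant hepatic impairment Child-Pugh class B or C according to the Child Pugh classification", and cites Appendix L for the classification.

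Section 7.5 says that subjects with clinically significant chronic hepatic impairment "at the time of Screening (Child- Pugh class C) are excluded from study participation". It recommends 280 mg daily for class A and 140 mg daily for class B, and advises against giving the drug in severe impairment. It cites Appendix D for the classification. Its table separates impairment already present at enrolment from impairment that develops during the study. It does so for classes A and B but not for class C, which appears only as developing on study, with the instruction to hold the drug.

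Other entry criteria also bear on the liver. Inclusion 7 requires "Adequate hepatic and renal function as indicated by all of the following" and sets limits on bilirubin and ALT. Inclusion 8 limits PT/INR and aPTT. Exclusion 9 covers "history of serious organ dysfunction or disease involving the heart, kidney, liver or other organ system" where the investigator considers that it puts the patient at undue risk.

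**The concern.** An eligibility criterion and the dosing section should describe the same population. Here a reader of section 4.2 would turn away a patient with clinically significant class B impairment. A reader of section 7.5 would find that patient absent from the screening exclusion and given a starting dose in the table.

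The stakes are eligibility and safety, not inference. Inclusion 3 requires that patients have no treatment indication, so there is little reason to accept avoidable exposure. Section 6.4 reports single-dose AUC 8.2-fold higher in class B than with normal liver function. If staff relied on section 7.5, the result would be an ineligible enrolment in a population where drug exposure may be raised.

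**Working it through.** **1. The two rules side by side.**

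| Class | Exclusion 20 (section 4.2) | Screening sentence (7.5) | Table (7.5), present at enrolment | Table (7.5), develops on study |
|---|---|---|---|---|
| A | not named | not named | 280 mg | 280 mg |
| B | excluded | not named | 140 mg | 140 mg |
| C | excluded | excluded | no column | hold until class B or better |

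The table header is broken in the extracted text, but its five dose entries match five sub-columns in order, which gives the assignment above. Two cells conflict with exclusion 20: the class B screening entry and the class B dose at enrolment. The remaining cells are consistent with it. In particular, 140 mg for class B that develops on study is needed under either rule.

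**2. How many patients.** The documents give no Child-Pugh class B prevalence for this population. The nearest figure is in section 7.5: 12 of 1,202 subjects in the population PK analysis had moderate impairment.

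- Proportion: 12/1,202 = 0.998%.
- Exact (Clopper-Pearson) 95% interval: 0.52% to 1.74%.
- Expected among 50 patients (section 15.1: "A maximum of 50 patients will be enrolled in the study"): 50 × 0.00998 = 0.50, with a range of 50 × 0.0052 = 0.26 to 50 × 0.0174 = 0.87.
- One such patient is 1/50 = 2 percentage points of the denominator.

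These counts are before inclusions 7 and 8 and exclusion 9 remove anyone. The interval reflects sampling error only. It does not cover the difference between NCI criteria and Child-Pugh class, or between the PK population and this trial.

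**3. Exposure at the tabulated doses.** Section 6.4 gives single-dose AUC ratios against normal liver function of 2.7 for class A and 8.2 for class B. The standard dose is 420 mg. If exposure is proportional to dose:

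- Class B at 140 mg: 8.2 × 140/420 = 2.73 times the exposure of 420 mg with normal liver function.
- Class A at 280 mg: 2.7 × 280/420 = 1.80 times.
- Class B relative to class A: 2.73/1.80 = 1.52.

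The protocol does not state proportionality. Section 6.4 says only that "exposure to ibrutinib increased as doses increased with substantial intersubject variability". Section 7.5 is also mixed on the direction: for mildly and moderately impaired subjects in the population PK analysis it says "These subjects did not show a significantly higher ibrutinib exposure compared with subjects with normal hepatic function", and then "In a hepatic impairment study, data showed an increase in ibrutinib exposure".

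**The case against.** The strongest reply has four parts.

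- **Section 4.2 governs entry.** Nothing in 7.5 declares class B eligible, and a site that applies exclusion 20 complies with both sections. This limits the risk. It does not explain why 7.5 gives a dose for class B present at enrolment and none for class C. Taken alone, the screening sentence might be merely incomplete; read with the table, it matches a class-C-only rule.
- **Exclusion 20 covers only active, clinically significant impairment.** On a narrow reading, class B impairment judged not clinically significant could enter, and the column would supply its dose. But 7.5 draws no such line. Its own exclusion for clinically significant impairment names class C only, and its class B column carries no qualifier. If that reading is intended, neither section says so.
- **The exposure arithmetic is not specific to this point.** This stands. The 2.73 applies equally to class B that develops on study, where 140 mg is retained. It indicates why class B entry matters but does not prove the conflict, and it depends on proportionality.
- **The prevalence figure is a rough transfer.** This also stands, because it uses NCI criteria in a pooled population. It shows only that few patients are likely to be involved.

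The other liver criteria do not replace exclusion 20. Inclusions 7 and 8 use laboratory limits with exemptions, exclusion 9 rests on the investigator's opinion, and none refers to Child-Pugh class.

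**Conclusion.** The conflict is real and lies in current, operative text. It is confined to two places in section 7.5: the screening sentence and the class B column for impairment present at enrolment. That conclusion comes from comparing the texts and needs no numerical assumption.

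The likely effect is small: about 0.5 patients in 50 (0.26 to 0.87) if the population PK proportion applies, and fewer after the other criteria. The sample size, power, significance level and primary test are unaffected. The point is worth correcting because the rule decides who is enrolled and dosed in a trial of patients who do not yet need treatment.

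A minor related point is that the two sections cite different appendices for the same classification. Neither appendix is in the text available for this review, so which citation is right cannot be settled here.

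**What to change.** Treat section 4.2 as governing and bring section 7.5 into line:

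- In the screening sentence, replace class C with class B or C.
- Delete the class B column for impairment present at enrolment.
- Keep 140 mg daily for class B that develops during the study.
- Check the appendix reference and cite one appendix in both sections.

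The sponsor should confirm the intended rule before the column is removed. If class B patients are meant to enter, amend exclusion 20 to class C only and leave the table as it is. If only class B impairment that is not clinically significant is meant to enter, both sections need to say so and define it.

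The cost is one sentence, one table column and one cross-reference in a protocol amendment. The sample size, analysis and visit schedule do not change.

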8.2. Medications to be Used with Caution

8.2.1 CYP3A- Inhibitors/Inducers

Ibrutinib is metabolized primarily by CYP3A. Concomitant use of ibrutinib and drugs that strongly or moderately inhibit CYP3A can increase ibrutinib exposure, and strong CYP3A inhibitors should be avoided.

Strong CYP3A inhibitors

Co-administration of ketoconazole, a strong CYP3A inhibitor, in 18 healthy subjects, increased exposure (Cmax and AUClast) of ibrutinib by 29- and 24-fold, respectively. In a dedicated drug-drug interaction study in subjects with B-cell malignancies, co-administration of voriconazole increased Cmax and AUC by 6.7-fold and 5.7-fold,

^{**} If further reduction is needed due to non-hepatic toxicity, ibrutinib should be held until resolution.

respectively. In clinical studies, the maximal observed ibrutinib exposure (AUC) was ≤2-fold in 37 subjects treated with mild and/or moderate CYP3A inhibitors when compared with the ibrutinib exposure in 76 subjects not treated concomitantly with CYP3A inhibitors. Clinical safety data in 66 subjects treated with moderate (n=47) or strong CYP3A inhibitors (n=19) did not reveal meaningful increases in toxicities. Voriconazole and posaconazole can be used concomitantly with ibrutinib. All other strong inhibitors of CYP3A (e.g., ketoconazole, indinavir, nelfinavir, ritonavir, saquinavir, clarithromycin, telithromycin, itraconazole, nefazodone, and cobicistat) should be avoided, and an alternative with less CYP3A inhibitory potential should be considered. If the benefit outweighs the risk and a strong CYP3A inhibitor must be used, please discuss recommendations for dosing with the PI and document the discussion in the medical record.

Moderate and mild CYP3A inhibitors

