8.3 Excluded concomitant therapy

Use of the following therapies is prohibited during the study:

- Any therapies intended for the treatment of lymphoma/leukemia whether FDAapproved or experimental (outside of this study)
- Radiotherapy (Note: Localized radiotherapy to an area not compromising bone marrow function is allowed)
- Steroid therapy for anti-neoplastic intent. Short courses (<=14days) of steroid treatment for non-cancer related medical reasons (e.g. joint inflammation, asthma exacerbation, rash, antiemetic use and infusion reactions) at doses that do not exceed 100mg per day of prednisone or equivalent are permitted.
- Strong CYP3A inhibitors which would be taken chronically, with the exception of voriconazole and posaconazole, as outlined in section 8.2.1.
- Grapefruit, Seville oranges, Star fruit
- Strong CYP3A inducers (e.g. rifampin, rifabutin, phenytoin, carbamazepine, and St. John's Wort) are not recommended
- The use of warfarin is not allowed during this study

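### Sections 8.2.1 and 8.3 allow voriconazole and posaconazole without carrying over the Section 7.5 ban on strong CYP inhibitors in chronic hepatic impairment

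*Combined protocol and SAP*

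**What the plan says.** Section 7.5 (dose modification in hepatic impairment) sets a rule by population, with no exception: "Concomitant use of strong CYP inhibitors is not permitted in subjects with chronic hepatic impairment". The same paragraph gives a dose for the mildest class: "For subjects with mild liver impairment (Child-Pugh class A), the recommended dose is 280mg daily".

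Section 8.2.1 sets rules by drug. It begins with the general position that "strong CYP3A inhibitors should be avoided". Under the strong-inhibitor subheading it then makes a specific allowance: "Voriconazole and posaconazole can be used concomitantly with ibrutinib". The sentence that follows deals with all the *other* strong inhibitors, so the protocol itself counts both azoles as strong. For those others there is a case-by-case route: "If the benefit outweighs the risk and a strong CYP3A inhibitor must be used, please discuss recommendations for dosing with the PI".

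Section 8.3 lists among the prohibited therapies: "Strong CYP3A inhibitors which would be taken chronically, with the exception of voriconazole and posaconazole, as outlined in section 8.2.1". Its only cross-reference is to 8.2.1.

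On who can be on study, exclusion 20 in Section 4.2 removes "Currently active, clinically significant hepatic impairment Child-Pugh class B or C according to the Child Pugh classification". Class A is not named there.

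**The concern.** A clinician or pharmacist who wants to know whether an antifungal is allowed will look in Section 8, the concomitant-therapy section. For voriconazole or posaconazole it says yes, whatever the subject's liver function. For a subject with chronic hepatic impairment, 7.5 says no. Nothing in Section 8 mentions hepatic impairment or sends the reader to 7.5, although 8.2.2 does send the reader to 8.4 on surgery.

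What is at stake is dosing safety in a few subjects. Each factor alone raises ibrutinib exposure in the protocol's own account: AUC was 2.7-fold in Child-Pugh A after a single dose (Section 6.4) and 5.7-fold with voriconazole (Section 8.2.1). Section 6.4 also reports a higher proportion of Grade 3 or higher adverse reactions in patients with mild impairment by NCI criteria. The protocol gives no figure for the two factors together.

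**Working it through.** This is a comparison of text. The plan gives no figure for the point, so there is none to reproduce.

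**Step 1. Can the subgroup be on study?** Yes. Exclusion 20 names only classes B and C, and 7.5 gives class A a dose of 280 mg. The 7.5 table also continues ibrutinib when class A (280 mg) or class B (140 mg) develops during the study, after entry screening has done its work. The ban reaches those later cases if the impairment is chronic.

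**Step 2. What does each section answer for voriconazole or posaconazole started on treatment?**

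| Subject | 7.5 | 8.2.1 | 8.3 |
|---|---|---|---|
| No hepatic impairment | silent | allowed | exempt from the prohibition |
| Chronic hepatic impairment | not permitted | allowed, no hepatic condition | exempt, no hepatic condition |

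The sections differ only in the second row.

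**Step 3. Does any text settle the second row?** No general order of precedence is stated. The one rule on discordance, in Section 12.1.2, concerns adverse-event recording and reporting. Exclusion 6 in Section 4.2 is an entry criterion. Section 6.0 prohibits strong inhibitors taken chronically, which leaves short courses open, and its examples include no azole. The azole dose reductions later in 8.2.1 are written for subjects with cGVHD. Section 5.1 recommends no azole, but 8.1 permits antifungal prophylaxis, so azole use is foreseeable.

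**Step 4. How many subjects?** The documents give neither a Child-Pugh A rate nor an azole-use rate, so this is an illustration on stated assumptions.

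- Maximum enrolment: 50 (Section 15.1).
- Impairment rate, upper: Section 7.5 reports that in a population PK analysis of 1,202 subjects "179 subjects (14.9%) had mild hepatic impairment according to National Cancer Institute criteria". Check: 179/1,202 = 0.149. It is a stand-in only, because the classification differs and the figure is not limited to chronic impairment.
- Impairment rate, lower: 2% (assumed).
- Use of either azole among impaired subjects: 1% to 10% (assumed).

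Expected number = 50 × impairment rate × azole-use rate.

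- Upper: 50 × 179/1,202 = 7.4 impaired subjects; × 0.10 = 0.74.
- Lower: 50 × 0.02 = 1 impaired subject; × 0.01 = 0.01.

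The entry limits on bilirubin, ALT and PT/INR in Section 4.1 point towards the lower end.

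**The case against.** The strongest reply is that nothing here is irreconcilable. A general permission and a narrower ban can both be obeyed: withhold strong inhibitors in impaired subjects and apply 8.2.1 to everyone else. A site that dosed a class A subject correctly has already read the 7.5 paragraph that holds the ban. Much of this stands. No sentence in Section 8 expressly allows an azole in an impaired subject, and 7.5 is the sensible rule to follow. It does not quite close the gap, though. Section 7.5 is specific by population, and 8.2.1 and 8.3 are specific by drug. Each can claim to be the special rule, and the text does not choose between them.

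Three further limits are fair:

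- **Reach of the ban.** Section 7.5 does not define chronic hepatic impairment, and the sentence just before the ban links clinically significant chronic impairment to class C, which is excluded. Covering class A is the more natural reading, since otherwise the ban would apply to almost nobody, but it is an inference. Section 7.5 also gives no reason for the ban, so a safety motive is inferred as well.
- **The PI route.** A reader might infer that 8.2.1 also opens the door to every other strong inhibitor in impaired subjects. The text does not support that. The route needs a benefit-risk judgement and a documented discussion with the PI, which is an individual check and barely a gap.
- **Evidence of harm.** Section 8.2.1 reports no meaningful increase in toxicities in 66 subjects on moderate or strong inhibitors, 19 of them on strong ones, with hepatic status not stated. Section 7.5 reports no significantly higher exposure in its NCI-mild and NCI-moderate groups.

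**Conclusion.** The point holds as a minor conflict of wording, confined to voriconazole and posaconazole in subjects with chronic hepatic impairment. That Section 8 lacks the limit is certain from the text. That the 7.5 ban covers class A subjects with chronic impairment is the most natural reading. On the assumed rates the expected number affected is about 0.01 to 0.74 of at most 50, so probably fewer than one. That range depends on the assumed azole use, the assumed 2% lower rate and a stand-in upper rate.

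A reader might be tempted to multiply the 2.7-fold and 5.7-fold AUC figures into a combined exposure. The documents do not say how the two effects combine, so no combined figure is supported and none is claimed. Nor do they support saying that patients are likely to be harmed. The primary endpoint, the sample size and the analysis in Section 15 are unaffected.

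**What to change.** Keep the 7.5 ban as it stands and make two insertions.

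1. At the head of the strong-inhibitor text in 8.2.1: *No strong CYP3A inhibitor, voriconazole and posaconazole included, may be given to a subject with chronic hepatic impairment (see 7.5).* This placement governs both the azole sentence and the PI route.
2. After the azole exemption in 8.3: *except where the subject has chronic hepatic impairment (see 7.5).*

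The cost is two short pieces of wording. As an amendment they need review and approval by the drug supplier and then IRB approval, and they can go with the next amendment. They add no procedures or patients, and they place no new restriction on care, because 7.5 already contains the ban.
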